7.3. Follow-up Observation of Adverse Events

Investigational-drug-related AEs that are ongoing at the end of follow-up period will be followed, in case that the principal investigator or sub-investigator judges the follow-up observation of AEs is clinically required.

The follow-up observation of AEs will be continued for 4 weeks after the end of follow-up period, and “date of resolution/resolving of AE” or “date of subject’s death” will be specified as the date of outcome confirmation.

If an AE has not resolved (have not been resolving or become stable) within 4 weeks after the end of follow-up period, the day of the first observation of AEs during the period ≥ 4 weeks after the end of following-up period will be specified as the date of outcome confirmation.

Table 13: Adverse Event Grading (Severity) Scale

Grade	Description
Grade 1 (Mild)	
 • Mild • Asymptomatic or mild symptoms • Clinical or diagnostic observations only • No intervention indicated
Grade 2 (Moderate)	
 • Moderate • Minimal, local or noninvasive intervention indicated • Limiting age-appropriate instrumental Activities of Daily Living (ADL)*¹
Grade 3 (Severe)	
 • Severe or medically significant but not immediately life-threatening • Hospitalization or prolongation of hospitalization indicated • Disabling • Limiting self care ADL*²
Grade 4 (Life-threatening)	
 • Life-threatening consequences • Urgent intervention indicated
Grade 5 (Death)	
 • Death related to AE

*1: Instrumental ADL; refers to preparing meals, shopping for groceries or clothes, using the telephone, managing money, etc.

*2: Self care ADL; refers to bathing, dressing and undressing, feeding self, using the toilet, taking medications, and not bedridden

7.4. Reporting of Serious Adverse Events

The principal investigator or sub-investigator (or designated staff) must submit an initial SAE report of any SAE to the Sponsor or CRO with any means of contact within 24 hours since knowing of the event.

The principal investigator must submit the follow-up SAEs report about the information on SAEs. A form provided in advance by the Sponsor or CRO or a form designated by the investigational site must be used, and submitted to the Sponsor or CRO, and the investigational site or site IRB. Follow-up SAE report will include any additional information or change in the information recorded in previous reports.

For contact information of the Sponsor and CRO, see “Organization and Structure of Clinical Study in Each Country and Region.”

8. DATA COLLECTION AND MANAGEMENT

8.1. Data Entry to Electronic Case Report Form (eCRF)

The principal investigator or sub-investigator (or designated staff) enters protocol-specified data into the eCRF by using the EDC system in this study; in an accurate, complete and easy-to-read manner at appropriate times, in English in principle. The study collaborators, other than the sub-investigator, who are designated by the principal investigator will be allowed only to transcribe data from the source documents into eCRF.

The principal investigator will review the data in eCRF, confirm the completeness and accuracy of data, and then provide an electronic signature in the predefined form in eCRF. In accordance with the investigational institution's own policy, the eCRF data that are exported in PDF will be retained at the site.

8.2. Correction or Change to Data in eCRF

If the principal investigator or sub-investigator (or designated staff) makes changes or corrections to data in the eCRF, the information on the former data before changes or corrections, persons who make changes or corrections, and date on which changes or corrections are made will be recorded in the audit trail in the EDC system. In any change or correction in the important data such as the date of obtaining the informed consent or the relationship between investigational drug and AEs, the reason for data changes or corrections should be specified and entered in eCRF.

The principal investigator will review the changes or corrections to data in the eCRF, confirm the data to be complete and accurate, and then provide an electronic signature in the predefined form in eCRF. In accordance with the investigational institution's own policy, the audit trail that is exported in PDF will be retained at the site.

The Development Sponsor or the data management CRO should review the data in eCRF in terms of data consistency, omission or apparent contradiction, or violation of GCP or the protocol. For a question resulting from the review, a query for a given data on eCRF will be created and sent to an investigational site. The principal investigator or sub-investigator (or designated staff) will respond to the queries by re-investigation and making changes or correction to data in eCRF if needed.

In this study, the changes or corrections to data in eCRF will not be made by a person designated by the Development Sponsor.

8.3. Data in eCRF as Source Data

The data entered in eCRF should match exactly the corresponding written record in source documents. The principal investigator will create a record that explains the reason for any inconsistency.

The data entered in eCRF may be qualified as the source documents, if a given data on eCRF itself is only source data; i.e., no written or electronic source document is existing. In this study, the data in eCRF may be qualified as source data if no source document exists for the items listed below and all of relevant comments:

- Subject background: ethnic background/race
- Primary disease:
 - Clinical symptoms caused by the primary disease (clinical symptoms associated with primary disease)
 - Clinical stage by the Ann Arbor classification
 - Prognostic risk group by International Prognostic Index (IPI)
 - Prognostic risk group by Prognostic Index for T-cell lymphoma (PIT)
- Medical history:
 - Concurrent diseases at the start of investigational drug dosing
 - Severity of drug sensitivity or allergy
- Pregnancy test: reason for the absence of pregnancy test
- 12-lead ECG: overall ECG findings (presence of abnormalities)
- Concomitant procedures: reason for starting therapeutic procedures
- Adverse Events (AEs):
 - Severity
 - Seriousness
 - Relationship to the investigational drug
 - Reason/rationale for denying the relationship

8.4. Deviations from the Protocol

The principal investigator or sub-investigator (or designated staff) should keep a record of all actions deviating from the protocol for any reason.

The principal investigator or the investigational site may deviate from or modify the protocol for medically justifiable reasons, without prior written agreement with the Sponsor and prior written IRB approval, such as when necessary to eliminate imminent hazards to the subject. However, the principal investigator should subsequently take procedures according to the regulatory requirements of each country or region in an expedited manner.

8.5. Committees and Coordinating Investigators

8.5.1. Pathological Review Committee

The Pathological Review Committee will consist of multiple pathologists who are not responsible for a medical expert, principal investigator or sub-investigator, coordinating investigator, or a member of another committee of this study. The Committee will be charged with the following tasks.

- Guidance and advice for the protocol and procedure for a central pathological diagnosis
- Guidance and advice for the procedures at central laboratory activities where pathology specimens are collected, stored and unstained tissue specimens are stained.
- Staining of unstained samples as needed

- Diagnosis by each member of the Pathological Review Committee (individual diagnosis)
- Central pathological diagnosis by the Pathological Review Committee (consensus diagnosis)

The histopathological classification based on World Health Organization (WHO) Classification Version 4 (2008) is used for the central pathological diagnosis at the Pathological Review Committee. If the central pathological diagnosis at the Pathological Review Committee differs from that at each investigational site, the central pathological diagnosis at the Pathological Review Committee will be given priority.

8.5.2. Efficacy and Safety Review Committee

The Efficacy and Safety Review Committee will consist of the hematologists and radiologists who are not responsible for a medical expert, principal investigator or sub-investigator, coordinating investigator, or a member of another committee of this study. The Committee will be charged with the following tasks.

- Guidance and advice for the protocol and procedure for a central assessment of tumor response
- Guidance and advice for the procedures at the Central Imaging Review Institution
- Central review based on the results of radiological assessment of tumor response at the Central Imaging Review Institution and the results of a local assessment of tumor response based on “non-imaging data” at each investigational site.
- Overall evaluation of efficacy and safety
- Advice for the termination/suspension of the study (appropriateness of continuation of the study)

The Efficacy and Safety Review Committee will be held to perform an interim review of efficacy and safety (and pharmacokinetics as needed) at the point when the number of subjects evaluable for efficacy reaches 20 and have all necessary data available.

8.5.3. Coordinating Investigators

At each country or region, in principle, at least one coordinating investigator will be assigned. The coordinating investigators will be charged with the following tasks, at request of the Development Sponsor. No committee will be organized.

- Guidance and advice for protocol development and revision
- Coordination among different countries/region participating in this study as for the content of protocol
- Coordination among different countries/region in this study as for interpretational questions about the protocol

9. STATISTICAL CONSIDERATIONS

9.1. Subsets

9.1.1. Handling of Subjects and Data

Prior to the analysis, the Development Sponsor will determine the handling (inclusion) of subjects based on the consultation with medical experts. If it is considered that data including laboratory values, 12-lead ECG or drug plasma or urine concentration measurements has been affected by abnormality of a sample (e.g. hemolysis or milky fluid) or a technical error, the Development Sponsor will decide, prior to the data analysis, whether or not to exclude that data from analysis based on the consultation with medical specialists.

9.1.2. Efficacy Analysis Set

A subject group consisting of subjects who fulfill eligibility criteria [See Section 3.1] and who take a tumor response assessment [See Section 6.14.2] at least one time after the administration of the investigational drug is defined as a "Full Analysis Set (FAS)". A subject group consisting of subjects who have no important protocol deviation including violation of eligibility criteria and/or dose and dosage that may affect the efficacy evaluation is defined as "Per Protocol Set (PPS)". FAS will be used for the primary analysis of efficacy endpoints, and PPS will be used for the secondary analysis of efficacy endpoints.

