2.5.2. Secondary Endpoints

Secondary endpoints of this study are as follows. "Response" is defined as "complete response (CR)" or "partial response (PR)".

- Progression-Free Survival (PFS)
Defined as the time from the first day of investigational drug administration (Day 1 of Cycle 1) to the date of "progressive disease (PD)" or "relapsed disease (RD)", or the date of "death", which occurs earlier
- Time To Response (TTR)
Defined as the time from the first day of investigational drug administration (Day 1 of Cycle 1) to the first day of tumor response observed for patients who achieved a CR or PR
- Duration of Response (DOR)
Defined as the time from the first day of tumor response observed for patients who achieved a CR or PR to the date of PD or RD, or the date of "death", which occurs earlier
- Overall Survival (OS)
Defined as the time from the first day of investigational drug administration (Day 1 of Cycle 1) to the date of "death" from any cause
- Occurrence of adverse events (AEs)
- Drug plasma concentration-time profile, PK parameters, and urinary excretion rates

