3. SUBJECT ELIGIBILITY

3.1. Inclusion Criteria

To be eligible for the study participation, patients must fulfill all of the following criteria:

- (1) Patients with ethnic background of each participating country/region;
- (2) Patients aged ≥ 20 years of age at the date of obtaining the informed consent;
- (3) Patients with histopathologically confirmed diagnosis of one of the following:
 - PTCL- not otherwise specified (PTCL-NOS);
 - Angioimmunoblastic T-cell Lymphoma (AITL);
 - Anaplastic Large Cell Lymphoma (ALCL), anaplastic lymphoma kinase (ALK) positive/negative);

The pathology specimens supporting the local diagnosis should be submitted for the central pathology review by the Pathological Review Committee [See Section 6.3].

- (4) Patients have a treatment history of at least one regimen with antitumor agents for the above diseases;
- (5) Patients have an enlarged lymph node or extranodal mass lesion that is measurable on computed tomography (CT);

In this study, a measurable enlarged lymph node is defined as a lesion of > 1.5 cm in greatest transverse diameter regardless of short axis measurement or > 1.0 cm in short axis regardless of greatest transverse diameter, that is clearly measurable in 2 perpendicular dimensions. A measurable extranodal mass lesion is defined as a lesion of ≥ 1.0 cm in greatest transverse diameter (two times longer than the scan slice thickness). A nodular mass within the liver or spleen is defined as a space-occupying lesion of ≥ 1.0 cm in 2 perpendicular dimensions.

- (6) Patients with Eastern Cooperative Oncology Group Performance Status (ECOG-PS) of 0, 1, or 2 [See Appendix 1]; and
- (7) Patients with a life expectancy of at least 3 months (e.g. no acute exacerbation of their primary disease) as determined by the principal investigator or sub-investigator.

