4.4.2. Study Withdrawal Criteria

A subject who meets any of the following criteria may be withdrawn from the study:

- (1) Request to withdraw consent;
- (2) Ineligibility found after enrollment;
- (3) Pregnancy;
- (4) Impossibility of continuation of protocol-specified examination, observation and investigation due to subject’s own reason; e.g., difficulties in visiting the investigational site due to subject’s change of residence;
- (5) Subject’s serious non-compliance with the protocol; with the principal investigator’s or the Sponsor’s judgement for not continuing the study in the subject;
- (6) Serious violation of GCP or significant deviation from the protocol; with the principal investigator’s or the study sponsor’s judgement for not continuing the study in the subject;
- (7) Death of the subject; or
- (8) At the discretion of the principal investigator or the Sponsor.

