4.4.3. Procedures for Study Withdrawal

In a subject who is withdrawn from the study before the first dosing of investigational drug, the subsequent examination, observation and investigation are not required to be performed.

In a subject who is withdrawn from the study after the start of investigational drug administration and cannot continue any of the subsequent examination, observation and investigation; as cases such as the subject is not willing to provide any own clinical data after the withdrawal of consent or the subjects is pregnant at a possible risk from protocol-specified examination, the principal investigator or sub-investigator will take the best measures to stop the study in the subject, under the condition where the subject’s safety is ensured. In case of subjects have ongoing AEs, the best measures to follow the ongoing AEs should be carried out where possible.

In a subject who is withdrawn from the study after the start of investigational drug administration; on the condition that the subject still has a willing to provide own clinical data, the subsequent examination, observation and investigation scheduled during the current cycle and the follow-up period should be completed.

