5 ANALYSIS SETS

5.1 Efficacy Analysis Set

The “full analysis set (FAS)” will consist of subjects who fulfill eligibility criteria (cf. Section 3 of protocol) and who take a tumor response assessment (cf. Section 6.14.2 of protocol) at least one time after the administration of investigational drug. A group of subjects who have no important protocol deviation including violation of eligibility criteria and/or dosage and administration that may affect the efficacy evaluation is defined as “per protocol set (PPS)”. FAS will be used for the primary analysis of efficacy endpoints, and PPS will be used for the secondary analysis of efficacy endpoints.

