5.2 Safety Analysis Set

A group of subjects who receive at least one dose of investigational drug is defined as the “safety analysis set (SAF)”. SAF will be used for the analysis of all subject characteristics, investigational drug administration and safety endpoints.

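### PFS and OS are analysed primarily in a set that requires a post-dose tumour assessment, so any eligible treated subject who dies unassessed is dropped and later survival is overstated

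*Protocol*

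**What the plan says.** Protocol 9.1.2 limits the FAS to subjects who meet the eligibility criteria and "who take a tumor response assessment [See Section 6.14.2] at least one time after the administration of the investigational drug". It then assigns the sets: "FAS will be used for the primary analysis of efficacy endpoints, and PPS will be used for the secondary analysis of efficacy endpoints". SAP 5.1 has the same definition and the same assignment ("FAS will be used for the primary analysis of efficacy endpoints").

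Protocol 9.4.3 places PFS and OS under efficacy endpoints and analyses them by Kaplan-Meier. SAP 11.6 adds the quartiles with 90% confidence intervals. Neither section names another analysis set. The all-treated set has other uses under SAP 5.2: "SAF will be used for the analysis of all subject characteristics, investigational drug administration and safety endpoints".

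Protocol 2.5.2 starts both clocks on Day 1 of Cycle 1. Death from any cause is the OS event. Under Protocol 9.4.3 and SAP 11.6, a death that comes before PD or RD is the progression date for PFS.

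Protocol 6.14.2 schedules the first assessment for Day 15 to 21 of Cycle 3. A subject who stops earlier is assessed between Day 15 and Day 42 of the last cycle.

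**The concern.** Entry to the FAS depends on something that happens after time zero. A subject must live long enough to be assessed, yet the survival clock starts at first dose. This is guaranteed survival time: the deaths most likely to be lost are the earliest ones. OS needs no scan at all, and the PFS rules already say what to do with a death that precedes progression. The analysis set then removes some of the events that those rules are written to capture.

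The trial has no control arm, so any overstatement passes straight into the reported PFS and OS estimates. No planned analysis of PFS or OS in all eligible treated subjects would reveal it. The PPS is defined by the absence of important deviations and does not serve that purpose.

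**Working it through.** **The plan's own figure.** The documents give no figure for PFS, OS, early deaths or unassessed subjects. The only related number is the sample size in Protocol 9.2: 55, raised to 65. An exact one-sample binomial calculation (threshold 10%, expected 25%, one-sided 5%, success at 10 or more responses of 55) gives type I error 0.0444 and power 0.911. With n = 54 and the same cut-off the power is 0.899. So 55 reproduces, and nothing in the sample size is disputed. The increase to 65 is for exclusions after central pathology; no allowance is stated for subjects without an assessment.

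**The window.** With 21-day cycles and no delay, Cycle 3 Day 15 to 21 is study Day 2 × 21 + 15 = 57 to 2 × 21 + 21 = 63.

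**The factor.** Let N be all eligible treated subjects and k those who die unassessed. Without censoring, at any time t after those deaths N × S_all(t) subjects are alive, and all remain in the count when the k are dropped. Hence

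S_FAS(t) = N × S_all(t) / (N − k) = S_all(t) × N/(N − k).

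The inputs k = 1, 3, 5 are assumptions. N = 65 is the planned number; N = 55 stands for some of the 65 being excluded by central pathology.

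| N | k | N/(N−k) | True 50% reported as |
|---|---|---|---|
| 65 | 1 | 65/64 = 1.016 | 50.8% |
| 65 | 3 | 65/62 = 1.048 | 52.4% |
| 65 | 5 | 65/60 = 1.083 | 54.2% |
| 55 | 1 | 55/54 = 1.019 | 50.9% |
| 55 | 3 | 55/52 = 1.058 | 52.9% |
| 55 | 5 | 55/50 = 1.100 | 55.0% |

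This step applies to PFS and OS alike, because the k deaths are events for both.

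**Quantiles, OS only.** Assume that survival in all eligible treated subjects is exponential with median M, and that the k deaths precede the quantile. Put f = (N − k)/N. The FAS curve reaches 0.5 where S_all = 0.5f, at time M × (1 − log2 f). The shift is −M × log2 f, and it is the same at every quartile. As a share of the median it is −log2 f. As a share of the lower quartile, which lies at 0.415M because log2(1/0.75) = 0.415, it is −log2 f / 0.415.

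| N | k | −log2 f | Median too long by | Lower quartile too long by |
|---|---|---|---|---|
| 65 | 1 | 0.022 | 2% | 5% |
| 65 | 3 | 0.068 | 7% | 16% |
| 65 | 5 | 0.115 | 12% | 28% |
| 55 | 1 | 0.026 | 3% | 6% |
| 55 | 3 | 0.081 | 8% | 19% |
| 55 | 5 | 0.138 | 14% | 33% |

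The model is not used for PFS, because progression dates cluster at the scan visits.

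**Check by simulation.** With N = 65, an assumed true median OS of 9 months, a 24-month cut-off and light censoring, 25%, 50% or 100% of deaths before Day 57 were dropped (on average 2.2, 4.3 and 8.6 subjects). The Kaplan-Meier median moved from about 9.0 to 9.4, 9.9 and 10.9 months. Across assumed medians of 6, 9 and 12 months, 12-month survival in the reduced set was not below that of all subjects in any of 27,000 simulated data sets. Dropping all such deaths is an upper bound.

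**The case against.** The strongest reply is that k should be small. Entry requires "Patients with a life expectancy of at least 3 months". Subjects who discontinue early are to be assessed in the last cycle. For a withdrawn subject who still provides data, "the subsequent examination, observation and investigation scheduled during the current cycle and the follow-up period should be completed". All of this stands and limits the number, but none of it helps a subject who dies first.

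The exclusion is also partly visible. SAP 10.1.2 counts both the FAS and the all-treated set, SAP 10.1.3 tabulates withdrawal reasons, and SAP 13 lists time-to-event and tumour response data. That allows a reader to suspect the problem but does not correct the estimate.

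The endpoints are secondary and descriptive, and precision is low. With about 60 subjects, uncensored and exponential (an assumption), the 90% interval half-width is roughly 31% of the median and 43% of the lower quartile. Every N = 65 figure above lies inside that. This limits the importance of the point, but imprecision does not excuse a one-directional bias.

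Protocol 9.1.1 and SAP 6 allow the handling of subjects to be settled before analysis. That is a case-by-case provision and does not replace the set definition.

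Some stronger readings are tempting but unsupported:

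- **That the estimates are biased whatever happens.** They are not if no eligible treated subject dies unassessed.
- **That every unassessed subject pushes the estimate upward.** Those who leave alive, for example under "Request to withdraw consent", have little effect on PFS and an uncertain one on OS.
- **That symptomatic progression is certainly lost from PFS.** Protocol 5.4.3, 6.14.2 and 6.15.1 leave open whether that judgement is itself a tumour response assessment.
- **That the lower quartile is too long by 39% or 50% when k = 5.** Those figures follow from putting the exponential on the FAS curve, which by its own definition is depleted of early deaths.
- **That earlier studies give k.** Protocol 1.3.1 reports 14 of 23 phase 1 subjects analysed for efficacy and 5 of 7 PTCL subjects evaluable, but gives no reasons, and the phase 1 rule also required two cycles.

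**Conclusion.** The concern holds in conditional form. The stated rule removes a valid PFS and OS event whenever an eligible treated subject dies before an assessment, and nothing else in either document restores it. For such deaths the direction is certain: survival at later times is overstated relative to all eligible treated subjects.

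The size cannot be derived from the documents. For one to five such deaths, a true 50% is overstated by about 1 to 5 percentage points. Under the exponential assumption for OS, the median is too long by 2% to 14% and the lower quartile by 5% to 33%. The larger percentage at the lower quartile reflects division of the same absolute shift by a shorter time.

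The change should be made, but it does not touch the primary conclusion, since no test or decision rule depends on PFS or OS. The same FAS condition also affects the response-rate denominator; that is a separate question and is not argued here.

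**What to change.** In Protocol 9.1.2 and 9.4.3 and in SAP 5.1 and 11.6:

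1. Make the primary set for PFS and OS all subjects who received at least one dose and meet the eligibility criteria as the FAS already applies them, without the post-dose assessment condition. The existing event rules for death and symptomatic progression then apply to everyone in that set.
2. Add a PFS censoring rule. The current one uses the most recent tumour assessment, which does not exist after dosing for an unassessed subject. Censor a subject with no post-dose assessment and no progression or death at Day 1 of Cycle 1. For OS, keep censoring at the last date known alive.
3. Keep the present FAS analysis as supportive.
4. Report how many eligible treated subjects had no post-dose assessment, with reasons.

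The cost is wording in two documents and one further analysis run. Survival status is already collected under Protocol 6.15.3. If such deaths occur, the PFS and OS estimates become less favourable.
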